6.3. Exploratory Objectives

To assess whether LY2951742 300 mg is superior to placebo as measured by:

- Proportion of patients randomized to LY2951742 meeting “very much better” or “much better” on the PGI-I at Month 9 and Month 15.
- Mean change in the weekly number of times of abortive medication use from baseline to each 2-week interval through Week 12 comparing LY2951742 with placebo.
- Change in percentage of times using oxygen from baseline for each 2-week interval through Week 12 comparing LY2951742 with placebo.
- Change in percentage of times using triptan from baseline for each 2-week interval through Week 12 comparing LY2951742 with placebo.
- Change in percentage of times of using acetaminophen/paracetamol or nonsteroidal anti-inflammatory drugs (NSAIDs) from baseline for each 2-week interval through Week 12 comparing LY2951742 with placebo.
- Responder analyses of LY2951742 compared with placebo from baseline to each 2-week interval through Week 12 for the proportion of patients meeting:
 - a 75% or greater reduction in the weekly cluster headache attack frequency
 - a 100% reduction in weekly cluster headache attack frequency
- Mean change from baseline to each 2-week interval through Week 12 in the cluster headache attack average weekly pain severity based on 5-point pain severity scale comparing LY2951742 with placebo.

© [REDACTED]

C
C
I

[figure not shown]
7. Investigational Plan

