4.3. Exploratory Objectives

To assess whether galcanezumab is superior to placebo as measured by:

- Proportion of patients randomized to galcanezumab meeting “very much better” or “much better” on the PGI-I at Month 9 and Month 15.
- Mean change in the weekly number of times of abortive medication use from baseline to each 2-week interval through Week 12 comparing galcanezumab with placebo.
- Change in percentage of times using oxygen from baseline for each 2-week interval through Week 12 comparing galcanezumab with placebo.
- Change in percentage of times using trip tan from baseline for each 2-week interval through Week 12 comparing galcanezumab with placebo.
- Change in percentage of times of using acetaminophen/paracetamol or nonsteroidal anti-inflammatory drugs (NSAIDs) from baseline for each 2-week interval through Week 12 comparing galcanezumab with placebo.
- Responder analyses of galcanezumab compared with placebo from baseline to each 2-week interval through Week 12 for the proportion of patients meeting:
 - a 75% or greater reduction in the weekly cluster headache attack frequency
 - a 100% reduction in weekly cluster headache attack frequency
- Mean change from baseline to each 2-week interval through Week 12 in the cluster headache attack average weekly pain severity based on 5-point pain severity scale comparing galcanezumab with placebo

● CCI

● CCI

5. A Priori Statistical Methods

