- Change from baseline in weekly total cluster headache attack duration will be calculated for each biweekly interval. Average duration of cluster headache attacks during a 24-hour period was asked in the ePRO diary. Patients were instructed to round up to the next duration selection with following choices: 15 minutes, 30 minutes, 1 hour, 2 hours, 3 hours, >3 hours. If the duration is >3 hours, then 4 hours will be imputed for the calculation of the total cluster headache attack duration. The total cluster headache attack duration for each interval will be calculated as the summation of the average duration of cluster headache attack multiplied by the number of cluster headache attacks in the day during the interval. If the total duration is more than 24 hours for a day, it will be set to 24 hours.
- The proportion of patients with a 30% or greater reduction from baseline in the weekly total cluster headache attack duration will be calculated for each biweekly interval.
- Change from baseline in weekly number of times of using oxygen as abortive medication at each interval will be calculated.

- Change from baseline in weekly number of times of using oral triptan, sumatriptan nasal spray, or zolmitriptan nasal spray as abortive medication at each interval will be calculated.
- Change from baseline in weekly number of times of using sumatriptan Sc as abortive medication at each interval will be calculated.
- Change from baseline in weekly number of times of using acetaminophen/paracetamol or NSAIDs as abortive medication at each interval will be derived.
- Change from baseline in number of times using oxygen as abortive medication per cluster headache attack at each interval will be derived. The endpoint at each interval will be calculated as follows:

$$\frac{\text{Total number of times using of oxygen during the interval}}{\# \text{ of cluster headache attack during the interval}}$$

- Change from baseline in number of times using oral triptan, sumatriptan nasal spray, or zolmitriptan nasal spray as abortive medication per cluster headache attack at each interval will be derived. The endpoint at each interval will be calculated as follows:

$$\frac{\text{Total number of times using the specified types of triptan during the interval}}{\# \text{ of cluster headache attack during the interval}}$$

- Change from baseline in number of times using sumatriptan Sc as abortive medication per cluster headache attack at each interval will be derived.

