- Change from baseline in number of times using acetaminophen/ paracetamol or NSAIDs as abortive medication per cluster headache attack at each interval will be derived. The endpoint at each interval will be calculated as follows:

$$\frac{\text{Total number of times using of acetaminophen/paracetamol or NSAIDs during the interval}}{\# \text{ of cluster headache attack during the interval}}$$

- Change from baseline in total weekly dose for oral triptan, sumatriptan nasal spray and zolmitriptan nasal spray combined will be derived. Total weekly dose will be calculated as follows:

$$\frac{\text{Sum of doses of oral triptan, sumatriptan nasal spray and zolmitriptan nasal spray during the interval} * 7}{\text{#####Number of nonmissing diary days during the interval}}$$

- Change from baseline in total weekly dose for sumatriptan Sc, oral triptan, sumatriptan nasal spray, and zolmitriptan nasal spray separately will be derived. Total weekly dose, respectively, will be calculated as follows:

$$\frac{\text{Sum of doses of sumatriptan Sc during the interval} * 7}{\text{\# of nonmissing diary days during the interval}}$$

$$\frac{\text{Sum of doses of oral triptan during the interval} * 7}{\text{\# of nonmissing diary days during the interval}}$$

$$\frac{\text{Sum of doses of sumatriptan nasal spray during the interval} * 7}{\text{\# of nonmissing diary days during the interval}}$$

$$\frac{\text{Sum of doses of zolmitriptan nasal spray during the interval} * 7}{\text{\# of nonmissing diary days during the interval}}$$

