Change from baseline to each 14-day interval (Weeks 1/2, 3/4, 5/6, 7/8, 9/10, 11/12)	No planned analyses	No planned analyses	1. Weekly average cluster headache attack pain severity in the remaining cluster headache attack days; 2. Weekly total cluster headache attack duration; 3. Weekly number of times using oxygen; 4. Weekly number of times using oral Triptan, sumatriptan nasal spray or zolmitriptan nasal spray; 5. Weekly number of times using sumatriptan Sc; 6. Weekly number of times using acetaminophen/paracetamol or NSAIDs; 7. Number of times using oxygen per cluster headache attack; 8. Number of times using oral triptan, sumatriptan nasal spray or zolmitriptan nasal spray per cluster headache attack; 9. Number of times using sumatriptan Sc per cluster headache attack; 10. Number of times using acetaminophen/paracetamol or NSAIDs per cluster headache attack; 11. Total weekly dose of oral triptan, sumatriptan nasal spray and zolmitriptan nasal spray combined; 12. Total weekly dose of sumatriptan subcutaneous; 13. Total weekly dose of oral triptan; 14. Total weekly dose of sumatriptan nasal spray; 15. Total weekly dose of zolmitriptan nasal spray.	Variables will be analyzed by a repeated measures analysis using a model as described in Section 5.5.8.1-5.5.8.3

Other Secondary and Exploratory Efficacy Variables and Their Derivation

Study Phase (SP) III	SP III and First Month of SP IV Combined	SP IV	Efficacy Variable	Analyses
Value at each visit (Visits 6, 8, 9, corresponding to Months 1, 2, 3)	No planned analyses	Value at each visit (Visits 16, 22, corresponding to Months 9 and 15)	1. Patient Global Impression of Improvement (PGI-I) Score	Variables will be analyzed by a repeated measures analysis using a model as described in Section 5.5.8.3 but without baseline covariate
Categorical variables at each 14 day-interval (Weeks 1/2, 3/4, 5/6, 7/8, 9/10, 11/12)	Categorical variables at each 14 day-interval (Weeks 1/2, 3/4, 5/6, 7/8, 9/10, 11/12, 13/14, 15/16)	No planned analyses	1. 30% Response 2. 50% Response 3. 75% Response 4. 100% Response 5. 30% reduction in weekly total cluster headache attack duration	For all variables, the visitwise percentages of patients meeting criteria will be compared between treatments using a categorical, repeated measures analysis described in this Section 5.5.8.3.

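### None of the four exploratory abortive-medication objectives has a derived variable matching its definition, and variable 11 adds doses of different triptans with no equivalence rule

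*SAP*

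**What the plan says.** **Objectives.** SAP 4.3 lists four exploratory items:

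- The first concerns overall use: "Mean change in the weekly number of times of abortive medication use from baseline to each 2-week interval through Week 12 comparing galcanezumab with placebo"
- The second is limited to oxygen and is put as a percentage: "Change in percentage of times using oxygen from baseline for each 2-week interval through Week 12 comparing galcanezumab with placebo"
- The third is its triptan counterpart, which Protocol 6.3 words as "Change in percentage of times using triptan from baseline for each 2-week interval through Week 12 comparing LY2951742 with placebo"
- The fourth treats simple analgesics in the same way: "Change in percentage of times of using acetaminophen/paracetamol or nonsteroidal anti-inflammatory drugs (NSAIDs) from baseline for each 2-week interval through Week 12"

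Neither document defines the denominator of the percentages. Nothing in the triptan objective excludes the subcutaneous form.

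**Derivations.** SAP 5.4.1.2 works class by class. For oxygen: "Change from baseline in weekly number of times of using oxygen as abortive medication at each interval will be calculated". For oral and nasal triptans: "Change from baseline in weekly number of times of using oral triptan, sumatriptan nasal spray, or zolmitriptan nasal spray as abortive medication". Subcutaneous sumatriptan and acetaminophen/NSAIDs have their own counts. The same four classes are then expressed per attack. Doses follow: "Change from baseline in total weekly dose for oral triptan, sumatriptan nasal spray and zolmitriptan nasal spray combined will be derived", and then separate weekly doses for subcutaneous sumatriptan, oral triptan and each nasal spray.

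**Analysis list.** In Table CGAM.5.4 (SAP 5.5.8.3), variables 3 to 6 are the weekly class counts and 7 to 10 the per-attack versions. The combined dose is "11. Total weekly dose of oral triptan, sumatriptan nasal spray and zolmitriptan nasal spray combined", and 12 to 15 are the separate doses. All are analysed by repeated measures.

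**History.** The SAP revision history for Version 4 says that the abortive-medication endpoints and their derivations were updated. The objectives in SAP 4.3 still carry the percentage wording.

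**The concern.** Two parts of the current SAP describe different measures, and nothing says which one governs the report. Followed literally, the plan produces no estimate or confidence interval for total abortive use. That is the one measure unaffected when a patient swaps one rescue drug for another at the same number of uses. Triptan use as a whole is never computed either.

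The combined dose is a separate matter. It adds amounts of sumatriptan, zolmitriptan and whatever oral triptans are taken as if they were on one scale, and it omits subcutaneous sumatriptan. A change in it may therefore reflect product choice and not need for rescue. Variable 13 has the same weakness if more than one oral compound is used. Protocol 9.8 allows oral triptans without naming a compound.

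**Working it through.** **1. Objectives against variables.** The plan states no figure to reproduce here, so the first check sets the sections side by side.

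| Objective (SAP 4.3, Protocol 6.3) | Nearest variables (Table CGAM.5.4) | Missing |
|---|---|---|
| Weekly uses, any abortive drug | 3, 4, 5, 6 separately | The total |
| Percentage of times, oxygen | 7 (uses per attack) | A percentage with a denominator |
| Percentage of times, triptan | 8 and 9 (per attack, split) | A percentage, and all triptans together |
| Percentage of times, acetaminophen/NSAIDs | 10 (uses per attack) | A percentage with a denominator |

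Matched as defined: 0 of 4. Partial counterpart: 3 of 4. Redaction does not explain the gap, because the table's 15 variables are numbered without a break.

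**2. Can the total be read off the planned output?** The four classes cover every drug that Protocol 9.8 allows, so at patient level total = v3 + v4 + v5 + v6. With invented counts, 10 + 6 + 4 + 2 = 22 falls to 5 + 3 + 2 + 1 = 11, a change of −11, which equals the sum of the class changes (−5 − 3 − 2 − 1). The precision of the treatment difference cannot be rebuilt from four separate models. Its variance is the sum of the four variances plus twice the sum of the between-class covariances, and those covariances are not reported.

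**3. Is uses per attack the same as a percentage of times?** No. Two uses in one attack give 2/1, or 200 per 100 attacks, so the ratio is not bounded by 100%. In the invented example, let attacks also halve from 20 to 10. Weekly oxygen use changes by −5. Oxygen per attack stays at 10/20 = 5/10 = 0.5, and oxygen as a share of all uses stays at 10/22 = 5/11 = 45.5%. These measures answer different questions. The per-attack ratio is also undefined in an interval with no attacks. SAP 5.4.1.2 sets pain severity to missing in that case but gives no rule for the per-attack ratios.

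**4. Combined dose with use held constant.** Let U be weekly uses and let all start on product A. A share s moves to product B, whose dose per use is r times that of A. The documents give no triptan doses, so r is an assumption.

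- Change towards the higher-dose product: [(1 − s)U + sUr]/U − 1 = s(r − 1)
- Change towards the lower-dose product: [(1 − s)r + s]/r − 1 = −s(1 − 1/r)

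| r (assumed) | s = 0.5, up / down | s = 1, up / down |
|---|---|---|
| 1 | 0% / 0% | 0% / 0% |
| 2 | +50% / −25% | +100% / −50% |
| 4 | +150% / −37.5% | +300% / −75% |
| 10 | +450% / −45% | +900% / −90% |
| 20 | +950% / −47.5% | +1900% / −95% |

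**5. A case that does not need r.** If a share s of oral/nasal uses moves to subcutaneous sumatriptan and the remaining dose mix is unchanged, variables 4 and 11 both change by −s: −25%, −50% or −100% for s = 0.25, 0.5 or 1. Any-triptan use changes by 0%.

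**The case against.** **The dose sum does not stand in for the objectives.** A reader might infer that it replaced them. It is one of 15 listed variables, beside eight use measures (3 to 10) and four separate doses (12 to 15). This objection stands.

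**Three objectives are not left without any analysis.** The Version 4 history suggests that uses per attack was meant to succeed the percentage of times. For oxygen and acetaminophen/NSAIDs the gap is then one of wording and denominator. This largely stands, but the SAP never says so, and total use and any-triptan use still have no variable.

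**Substitution is mostly visible.** A patient who moves from subcutaneous sumatriptan to oxygen goes down on variable 5 and up on variable 3, and both are reported. A reader might infer that switching is hidden, but the class counts show it. What they lack is one estimate, with its precision, of net use.

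**A false treatment effect needs more than switching.** Switching would have to differ between randomised arms, and the documents give no evidence of that. The large percentages in the working also need an assumed r and, at s = 1, a switch of every use. This stands. Nor do the documents show that the sum is clinically meaningless. They show only that no conversion rule is stated.

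**A share-of-uses percentage is not clearly better.** Shares also move in opposite directions under substitution and are undefined at zero use. This stands, so rewording the objectives is an equally good remedy.

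**Conclusion.** The mismatch is real. None of the four stated objectives has a variable of the same definition, three have a partial per-attack counterpart, and total and any-triptan use are never derived. The combined dose has no equivalence rule and excludes subcutaneous sumatriptan, so it can move with product choice alone. The direction of that argument needs no outside figure. For switches within the sum, the size rests on an assumed dose ratio and share switched. For a move to the subcutaneous form it rests only on the share and an unchanged dose mix.

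Consequences are limited. The endpoints are exploratory, lie outside the fixed sequence in SAP 5.5.1.4 and 5.5.8.2, and carry no multiplicity adjustment. No primary, gated or safety conclusion depends on them. This is an alignment correction to consider.

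**What to change.** In SAP 5.4.1.2 and Table CGAM.5.4:

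1. Add the weekly number of uses of any abortive medication, as the patient-level sum of variables 3 to 6, and analyse it with the same repeated measures model.
2. Add the weekly number of uses of any triptan, as variable 4 plus variable 5.
3. Either define the percentage objectives, with their denominator and a rule for a zero denominator, or reword them in SAP 4.3 as uses per attack, with a rule for intervals that have no attacks. Align Protocol 6.3 or record the difference.
4. Drop variable 11, or state a conversion rule and label it descriptive. Limit variable 13 to one compound, or treat it the same way.

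SAP Appendix 2 lists as a deviation that oxygen use was not reported as a number of times. Item 1 should say how such records enter the total.

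The cost is some SAP wording, a few sums of variables already derived from the diary, and the loss or relabelling of at most two dose outputs. No new data are needed.

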5.4.1.3. Patient Global Impression of Improvement Endpoint

The Patient Global Impression of Improvement (PGI-I) requests patients to mark the box that best describes their cluster headache condition since they started taking this medicine. The options in the displayed boxes are represented on a 7-point scale, with 1=very much better and 7=very much worse (Guy 1976).

The patient-reported PGI-I information will be captured at office visits. If the PGI-I collection date is greater than 10 days from the visit date, the record will not be used for analysis.

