(Visits 4 and 7) with the patient approximately 1 week after the first two IP administration visits during SP III to collect spontaneously reported AEs. At Visit 5, the patient will come into the office for the collection of blood samples 2 weeks after the first dose. During SP III, the patient will continue to record his or her cluster headache attack information daily in the ePRO diary.

- For patients who discontinue early in SP III, they should enter SP V.
- For patients who complete SP III, SP IV is an optional 1-year exposure, open-label treatment phase which is described below.
- For patients who choose not to enter SP IV, they should enter SP V.

During SP IV, the unblinded site personnel will continue to prepare the IP for each patient. All patients who enter SP IV will receive open-label monthly injections of LY2951742. All study procedures at Visit 9 must be completed prior to patients receiving the first dose of LY2951742 in SP IV. Patients and investigators will remain blinded to the SP III treatment assignments during SP IV. Each dose of IP will be administered as 3 SC injections at office visits: Visits 9 and 11 through 21. Since placebo patients will be transitioning to LY2951742 at Visit 9, all patients should remain in the office for 30 minutes for observation after administration of IP. Also, during SP IV, some patients may transition to LY2951742 300 mg supplied in 3 prefilled syringes with each syringe containing 100 mg. These patients should remain in the office for 30 minutes for observation after the first prefilled syringe injection. All patients will continue to record his or her cluster headache attack information daily in the ePRO diary until Visit 11.

Study Phase V is a 16-week post-treatment phase for safety follow-up.

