9.5. Selection and Timing of Doses

Patients in this study will be assigned to 1 of 2 treatment groups: placebo or LY2951742 300 mg. Investigational product (LY2951742 or placebo) will be administered as 3 SC injections every 30 days for a total of 3 administrations during SP III.

During SP IV, LY2951742 will be administered as 3 SC injections every 30 days for a total of 12 administrations.

Investigational product injections should be administered after all other study procedures are completed for the given visit.

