4.2.2. Other Secondary Objectives

- To assess whether galcanezumab 300 mg is superior to placebo on the following:
 - Mean change in the weekly cluster headache attack frequency from baseline to each 2-week interval through Week 12.
 - The proportion of patients with a 50% or greater reduction in the weekly frequency of cluster headache attacks from baseline at each 2-week interval through Week 12.
 - The proportion of patients with a 30% or greater reduction in the weekly frequency of cluster headache attacks from baseline at each 2-week interval through Week 12.
 - Proportion of patients reporting a score of 1 (“very much better”) or 2 (“much better”) on the Patient Global Impression of Improvement (PGI-I) at Month 1, Month 2, and Month 3.
- To compare galcanezumab with placebo on the following safety and tolerability measures:
 - spontaneously reported treatment-emergent adverse events (TEAEs)

- serious adverse events (SAEs)
- adverse events leading to discontinuation
- suicidal ideation and behaviors assessed by solicited questioning using the C-SSRS.
- To assess the development and consequences of anti-drug antibodies (ADA) to galcanezumab in patients exposed to galcanezumab; to provide samples for subsequent evaluation of neutralizing ADA (Nab).
- To evaluate the pharmacokinetics (PK) of galcanezumab.

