Categorical variables at each visit (Visits 6, 8, 9, corresponding to Months 1, 2, 3)	No planned analyses	Categorical variables at each visit (Visits 16, 22, corresponding to Months 9 and 15)	1. Proportion of patients reporting a score of 1 ("very much improved") or 2 ("much improved") on Patient Global Impression of Improvement (PGI-I)	For all variables, the visitwise percentages of patients meeting criteria will be compared between treatments using a categorical, repeated measures analysis described in this Section 5.5.8.3 but without baseline value covariate

Abbreviations: NSAIDs = nonsteroidal anti-inflammatory drugs; SP = study phase.

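### The SAP's 10-day PGI-I rule has no pre-dose condition at Visit 9, so a late Month 3 rating made after the first open-label dose would be kept as a double-blind result (minor)

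*SAP*

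**What the plan says.** SAP 5.4.1.3 says where the PGI-I is collected: "The patient-reported PGI-I information will be captured at office visits". It then gives its only record-selection rule: "If the PGI-I collection date is greater than 10 days from the visit date, the record will not be used for analysis". The rule states no direction, makes no exception for any visit and does not mention dosing.

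SAP Table CGAM.5.4 (section 5.5.8.3) uses the double-blind PGI-I in two ways. The score is analysed as "Value at each visit (Visits 6, 8, 9, corresponding to Months 1, 2, 3"), and the response as "Categorical variables at each visit (Visits 6, 8, 9, corresponding to Months 1, 2, 3"). Response at these three time points is an other secondary objective in SAP 4.2.2: "Proportion of patients reporting a score of 1 (“very much better”) or 2 (“much better”) on the Patient Global Impression of Improvement (PGI-I) at Month". It is not gated, and SAP 5.5.1 applies no multiplicity adjustment to it.

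Visit 9 is also where the open-label extension (SP IV) starts dosing. Protocol 7.1 notes: "Since placebo patients will be transitioning to LY2951742 at Visit 9, all patients should remain in the office for 30 minutes". The same section fixes the order of events: "All study procedures at Visit 9 must be completed prior to patients receiving the first dose of LY2951742 in SP IV". Protocol 9.5 gives the general form: "Investigational product injections should be administered after all other study procedures are completed for the given visit".

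**The concern.** A tolerance of 10 days around the visit date is harmless when treatment is the same on both sides of the visit. At Visit 9 it is not. A placebo patient who enters SP IV changes to galcanezumab on that day, and patients in both arms then know they are receiving active drug. A rating made after the injection but within 10 days passes the SAP's filter and is analysed as a Month 3 double-blind value.

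Two effects are possible. Placebo ratings could pick up some benefit of active drug, which narrows the treatment difference. Knowledge of the current open-label treatment could also shift ratings in either arm, in a direction and by an amount that cannot be stated from the documents. The item itself offers no protection, because it asks for change since treatment began and does not confine the answer to the double-blind phase (SP III).

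**Working it through.** The documents give no sample-size, power or response-rate figure for PGI-I, so there is no stated figure to reproduce. The check is date arithmetic, a comparison of rules, and an illustration under stated assumptions.

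**1. Which visits can mix phases.** Nominal days come from the study schedule (Protocol Attachment 1). The accepted range is the visit day plus or minus 10.

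- Visit 6: Day 30, accepted Days 20 to 40, inside SP III.
- Visit 8: Day 60, accepted Days 50 to 70, inside SP III.
- Visit 9: Day 90, accepted Days 80 to 100. The last 10 days follow the nominal first open-label dose and run 3 days past the Visit 10 telephone call (Day 97).

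Only Visit 9 is affected.

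**2. What has to happen for a post-dose record to exist.** The rating must slip past the injection, against Protocol 7.1 and 9.5. It must then be collected off schedule: Visit 10 is a telephone contact for adverse events, the next office visit is Visit 11 (Day 120), and the next scheduled PGI-I in SP IV is Visit 16 (Day 270).

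**3. How the SAP treats other data at the same boundary.**

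- Diary (5.4.1.2): for patients who continue, Weeks 11/12 stop the day before the first open-label injection.
- Adverse events (Table CGAM.5.3): the SP III window closes at Visit 9 before dosing. Section 5.5.9.1.1 uses a CRF flag for events on the day of first open-label treatment.
- C-SSRS, laboratory, vital signs and ECG (Table CGAM.5.3): through Visit 9, with no pre-dose wording.
- PGI-I: no pre-dose wording, plus an explicit rule that keeps off-date records.
- Deviations (Appendix 2): late PGI-I collection is not listed, although 5.5.3 lets the team add nonprogrammable categories.

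**4. Size, as an illustration.** Let p_P and p_G be the true Month 3 response rates on placebo and galcanezumab. Let f be the share of analysed placebo ratings that are post-dose, and s the part of the gap (p_G - p_P) that those raters gain.

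Observed placebo rate = p_P + f × s × (p_G - p_P).

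Observed difference = (1 - f × s) × (p_G - p_P).

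With s = 1 this is (1 - f) times the true difference. Assume a true difference of 20 points:

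| f | s = 0.5 | s = 1 |
|---|---|---|
| 5% | 19.5 | 19.0 |
| 10% | 19.0 | 18.0 |
| 20% | 18.0 | 16.0 |

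For scale, the planned minimum of 162 patients randomised 1:1 gives 81 per arm. If all 81 placebo patients have a Month 3 rating, one late record has f = 1/81 = 1.2% and moves a 20-point difference by at most 20/81 = 0.25 points. An f of 5% would need about four such patients (81 × 0.05 = 4.05).

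**The case against.** The strongest reply is that the documents already prevent this in conduct. The PGI-I is an office-visit assessment, it must precede the injection, and no later contact within 10 days is scheduled to collect it. A rating dated after Visit 9 is also not by itself post-dose: if the procedures slip, the dose should slip with them. Other visit-based SP III measures rely on the same ordering without a pre-dose clause, whereas diary and adverse event data run continuously across the dose and have to be cut. All of this stands, and it makes the event unlikely.

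It does not close the gap. The 10-day rule exists to handle ratings that were not made on the visit date. In that situation the ordering may already have failed, and the SAP then keeps the record.

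A reader might infer more than the documents support:

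- That post-dose ratings are planned or expected. They are not; each would breach the protocol's order.
- That late raters are unblinded. They would know that they now receive open-label galcanezumab, but Protocol 7.1 keeps the SP III assignment blinded during SP IV.
- That the attenuation figures estimate the bias. Neither f nor the response rates are in the documents. Taking s = 1 requires a placebo patient to reach the full drug response rate within 10 days of one dose, on an item that also covers about 90 days on placebo.

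**Conclusion.** The gap in the record-selection rule is real and minor. If a Visit 9 PGI-I is collected 1 to 10 days late in a patient already dosed in SP IV, the SAP counts it as the Month 3 double-blind result.

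The reach is one of three double-blind time points, in patients entering SP IV only, for the PGI-I score and response. The primary and gated endpoints are untouched. For late placebo ratings the likely direction is toward no difference. The factor (1 - f) bounds the loss only on the assumption that late placebo raters gain no more than the drug response rate; expectation effects in either arm are not quantified. The number of affected records is unknown and, given the protocol's ordering, probably small. The case for changing the SAP is that the change is cheap, not that a conclusion is likely to turn on it.

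**What to change.** Add to SAP 5.4.1.3: for patients entering SP IV, a Visit 9 PGI-I is used for Month 3 only if its collection date is on or before the date of the first open-label injection. Accept same-day records on the strength of the protocol's procedure-before-injection order, or check them by time-stamp if the PGI-I record has one; the documents do not say that it does. Treat later records as missing and report how many are removed, by arm. Keep the 10-day rule unchanged otherwise.

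The programming needs one condition on data already collected: the PGI-I collection date, and the injection date and time recorded on the eCRF (SAP 5.5.5). The downside is that a few Month 3 ratings become missing; those patients still contribute any Month 1 and Month 2 ratings to the repeated measures model. No study procedure changes.
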